6.2.a. ω-3 fish oil and placebo (corn oil) are obtained by Epax in 0.7 g gel caps and they have identical shape, color, taste and weight. Each 0.7 g of fish oil ω-3 contains 400 mg eicosapentaenoic acid (EPA) and 200 mg docosahexaenoic acid (DHA). We start with 1.4 g/day of fish oil and continue until the 6 month visit. If the average of IL-6 measured at 3- and 6-month visits does not **decrease by ≥40%** vs. baseline (average of screening visits 1 and 2), we increase the dose to 2.8 g/day. To limit the effect of within subject variation, we use the average of 2 measures. If there is an acute illness within one month prior to the visit, the 3-month or the 6-month IL-6 measure is postponed or excluded from titration algorithms. In previous RCTs, ω-3 reduced IL-6 by >50% using 1 to 2 g/day of fish oil.^{75, 76} In other trials in elders, fish oil was used in comparable doses

ranging from 0.6 to 2.3 g/day.⁶²

6.2.a.1. Risks and risk protection and dose adjustments related to administration of ω -3

There are no contraindications to the use of ω -3 fish oil, except intolerance or allergy to fish oil. ω -3 are considered very safe and produce only mild adverse effects involving gastrointestinal upset and fishy aftertaste.^{148, 149} FDA has affirming menhaden fish oil as **Generally Recognized As Safe (GRAS)** under 21 CFR 4 184.1472 provided that the daily intake of EPA and DHA combined do not exceed 3 g per person per day. <http://www.accessdata.fda.gov/scripts/cdrh/cfdocs/cfcfr/CFRSearch.cfm?fr=184.1472> and <http://www.fda.gov/Food/IngredientsPackagingLabeling/GRAS/SCOGS/default.htm> accessed on 9/11/2014.

ω -3 may rarely cause clinical or subclinical bleeding, worsening of glycemic control in people with impaired glucose tolerance, rise in LDL cholesterol, and possibly hypotension when combined with antihypertensive treatment.

We start with a dose of 1.4 g/day of ω -3 fish oil. Adverse effects, such as gastrointestinal discomfort are monitored. Dose will be adjusted as below based on serum glucose, LDL cholesterol and hemoglobin measured at baseline and at month 3, 6, and 9. ω -3 fish oil dose will be decreased or discontinued if any of the following criteria are met at follow-up:

- New onset paroxysmal or persistent atrial fibrillation
- Hemoglobin decreases by $\geq 20\%$ from baseline (dose will be discontinued),
- The participant is not diabetic and fasting glucose is > 126 AND has increased by $>30\%$ from baseline,

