- The participant is diabetic and fasting glucose > 300 ,
- Baseline LDL > 130 AND increases by $\geq 20\%$ from baseline,
- The participant is taking a blood pressure lowering agent OR is also participating in the Losartan arm of the study AND blood pressure is $<90/50$, or
- Participant does not tolerate the fish oil.

The principal investigator/study physician at each site has the discretion to opt out of ω -3 fish oil dose adjustments due to glucose and/or LDL levels.

We increase the dose of ω -3 fish oil to 2.8 g/day if the average of IL-6 measured at 3- and 6-month visits has not **decreased by at least 40%** vs. baseline (average of screening visits 1 and 2). The 40% threshold is selected based on previous trials with ω -3 fatty acids. ω -3 fatty acids have been shown to reduce IL-6 by $>50\%$ in RCTs^{75, 76} and to be consistent with the threshold used below for losartan. To minimize the impact of outliers due to acute illness, the 3-month or the 6-month IL-6 measure are excluded or postponed if there is an acute illness within one month prior to the visit. In the rationale for dose titration we use the following assumptions:

1. IL-6 biovariation as a CV is $\sim 30\%$. This is a reasonable estimate based on our own estimates (unpublished data) and those of others.^{150, 151} This means that a SD of each person's day to day variability is about 30% of the mean value.
2. We have two measures at baseline that can be averaged to yield a reasonable estimate of each person's average value.
3. For dose adjustment we use IL-6 measured at 3 months and 6 months.
4. The half-life of IL-6 is extremely short (<30 minutes), so response to interventions is essentially coincident to the effect of the interventions.
5. We screen for outliers by excluding participants who experienced an acute illness within a month of the visit

6.2.b. LO and placebo (cellulose based) are obtained in 25 mg and 50 mg capsules. The shell capsules are cellulose based. Placebo and LO have identical shape, color, taste and weight. We start with 25 mg/day, if tolerated, we step up to 50 mg/day. If there are no safety concerns, we continue with 50 mg/day until the 6 month visit. If the average of IL-6 measured at 3- and 6-month visits does not **decrease by $\geq 40\%$** vs. baseline (average of screening visits 1 and 2), we increase the dose to 100 mg/day. Equivalent doses of ARBs have shown to reduce IL-6 by $>40\%$ ^{77, 78} and by 58% ⁷⁹ in RCTs.

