From LIFE-Pilot, the SD of 400 m walk speed in IL-6 eligible participants is 0.21 m/s, with high correlation ($r > 0.80$) between baseline and 12 month measures. With at least 60 and 75 participants per group (for pairwise comparisons), we project to have >99% power to detect a difference in means of >0.095 m/sec using a one-sided test at the 10% level (a substantial meaningful change).¹⁹² There is also 67% power to detect a >0.038 m/sec difference (a small meaningful change). Using groups of 135 and 165 (for main effects), we would have >99% power to detect >0.095 m/sec, and 86% power for a difference >0.038 m/sec in walking speed. This analysis uses linear mixed models, as for IL-6; a similar approach is used for the secondary outcomes of SPPB, frailty, and grip strength. This achieves the last part of Aim a (i). For people who are unable to complete the 400m walk, we will use their walking speed from the portion completed.

6.10.c. Associations between inflammation and function

We base our calculation of detectable SPPB effects on LIFE data. The correlations between baseline and 24 month follow-up SPPB outcomes were 0.49 (Successful Aging: SA) and 0.47 (Physical Activity: PA); we assume a correlation of 0.5 between baseline and 12 month in ENRGISE. Estimated standard deviations at 24 months were 2.60 (SA) and 2.47 (PA); we assume 2.5. Under these assumptions, for the comparisons of 60 to 65 people, we have 90% power to detect a difference of at least 0.99 SPPB units; for the comparisons of 135 to 165 people, we have 90% power to detect a difference of at least 0.66 SPPB units. Both assume 1-sided tests at the 10% level.

We will examine the relationship between the change in IL-6 and the change in walking speed using univariate regression. Assuming we assess ≥ 285 participants (of 300, $\geq 95\%$) at 12 months, we have 80% power to detect a correlation less than -0.126 (i.e. at least 1.59% of explained variability) using a one-sided test at the 10% level. We have 90% power if the correlation is less than -0.152 (Aim a (iii)).

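### The planned regression of walking-speed change on IL-6 change makes no allowance for within-person IL-6 variation, so the slope that feeds the main-trial decision is biased toward zero

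*Combined protocol and SAP*

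**What the plan says.** Section 6.10.c states: "We will examine the relationship between the change in IL-6 and the change in walking speed using univariate regression". It is sized on at least 285 of 300 participants assessed at 12 months, with a one-sided test at the 10% level: "we have 80% power to detect a correlation less than -0.126", and "We have 90% power if the correlation is less than -0.152". The section does not give the scale of the IL-6 change (raw or log), the definition of baseline, or the follow-up draws used. It plans no correction for measurement variation in the predictor.

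Elsewhere the plan recognises that variation. The titration assumptions in section 6.2.a.1 take the CV to be about 30%: "This means that a SD of each person's day to day variability is about 30% of the mean value". For titration, section 6.2.a says: "To limit the effect of within subject variation, we use the average of 2 measures". Section 6.6 likewise uses the mean of two screening draws for eligibility. Section 6.10.c also compares the two screening draws with a Bland-Altman plot, but the result is meant for eligibility and participant risk in the main trial, not for this regression.

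Estimating how strongly the two changes are related is goal 4 of the pilot (section 6.1). Section 6.10.e lists that relationship among the inputs to the choice of what goes forward.

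**The concern.** When a predictor is measured with independent random error, ordinary regression shrinks its slope by the predictor's reliability and shrinks the correlation by the square root of the reliability. A change score is especially exposed, because it carries the noise of both baseline and follow-up. With a 30% CV, that noise is large relative to the only spread figure the plan gives for log(IL-6).

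At stake is how the pilot result will be read. The decision in section 6.10.e concerns how strongly walking speed follows a real change in IL-6. An uncorrected slope answers a diluted version of that question and could make a real relation look too weak to pursue. A test of no association that remains valid does not remove this problem, because the strength of the relation is weighed, not only its significance.

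**Working it through.** **1. The plan's power figures.** With n = 285 and a one-sided 10% test, power = Φ(atanh(|r|)·√(n−3) − 1.2816).
- r = 0.126 gives 80.1%.
- r = 0.152 gives 90.2%.
- 0.126² = 1.59%, as stated.

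Both figures reproduce.

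**2. Noise in the measured change.** With a CV of 30% (section 6.2.a.1), the log-scale variance of one draw is ln(1 + 0.3²) = 0.0862. A two-draw baseline and one 12-month draw, which is a reading of the text, give 0.0862 × (1/2 + 1) = 0.129. With a single-draw baseline it would be 0.0862 × 2 = 0.172.

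**3. Total variance of change.** The documents do not give this. Section 6.10.b gives a LIFE-P root mean squared error of 0.52, adjusted for baseline and treatment, so its square is 0.2704. If it carries over, Var(change) = 0.2704 + (1−b)²·SD², where b is the slope of follow-up on baseline log(IL-6) and SD is the baseline log SD. Neither b nor SD is in the documents, so both are assumptions:
- Narrow: b = 0.5 to 0.9 and SD = 0.35 to 0.45 give a total of about 0.27 to 0.32.
- Wide: b = 0.4 to 1.0 and SD = 0.3 to 0.7 give a total of 0.27 to 0.45.

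**4. Dilution.** Reliability L = 1 − 0.129/total. The slope is multiplied by L and the correlation by √L. The equivalent error-free correlation is the stated one divided by √L.

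| Total variance | Noise share = slope loss | L | Correlation loss | Error-free r for 80% power | Error-free r for 90% power |
|---|---|---|---|---|---|
| 0.27 | 48% | 0.52 | 28% | -0.174 | -0.210 |
| 0.32 | 40% | 0.60 | 23% | -0.163 | -0.197 |
| 0.45 (wide extreme) | 29% | 0.71 | 16% | -0.149 | -0.180 |

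A simulation of 8,000 trials at the first row gave a slope ratio of 0.52 and a type I error of 9.5%.

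**5. Treatment effects.** Pooling the arms adds true variance. Take 45% of participants on each drug (135 of 300), with the two allocations treated as independent, and add the treatment variance to 0.2704. The noise share is then 46% if each drug lowers IL-6 by 15%, and 32% if by 40%. Both lie within the wide range.

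**6. Averaging four follow-up draws.** Noise falls to 0.0862 × (1/2 + 1/4) = 0.065. If true change is the same at every visit, L rises from 0.52 to 0.141/(0.141 + 0.065) = 0.69. Suppose instead that true changes correlate at ρ between visits and walking speed follows the month-12 value. Averaging then beats the single draw only when ρ exceeds about 0.75 to 0.8. At ρ = 0.7 and total variance 0.27, power at an error-free -0.126 falls from 60% to 58%.

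**The case against.** A reader might infer that the stated 80% and 90% power are wrong and should read about 60-64% and 72-76%. The documents do not support that. The regression tests the correlation between measured changes, the plan's figures are right for that quantity, and the test keeps its size. The lower figures apply only to error-free correlations of -0.126 and -0.152, for which the plan never states power. What stands is that the text does not say which correlation it means.

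A reader might also infer that nearly half of the measured change is noise by the plan's own CV. The CV alone gives no share. A total variance is needed, and 0.52 is a residual SD from another study, not an SD of change. With a two-draw baseline, 48% is the top of the range.

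The single 12-month draw is likewise inferred. Table 6.3 also schedules IL-6 at months 3, 6 and 9, and the mixed-model wording in section 6.10.d can be read as covering IL-6 too. Nor do the documents say that raw change will be used: section 6.10.c is silent on scale, while 6.10.b and 6.10.d work with log(IL-6). These points make the size uncertain and call for clarification. They do not remove the bias, because no reading includes a stated correction.

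Finally, section 6.10.e sets no threshold on this slope and weighs it with other evidence, and the draws needed for a later correction are already planned. That limits the consequence and keeps the remedy cheap.

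**Conclusion.** The concern holds as one of uncorrected dilution. The observed slope is biased toward zero by about 40-48% if the variance of log change is 0.27 to 0.32, and by about 29-48% under wider assumptions. The correlation loses about 23-28%, or as little as 16% at the wide extreme. The stated power is correct for measured change. Expressed as error-free correlations, the detectable values are about -0.15 to -0.17 (80%) and -0.18 to -0.21 (90%).

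This rests on the 30% CV, a two-draw baseline with one 12-month draw, noise that is independent between draws and unrelated to walking speed, and the LIFE-P residual of 0.52 carrying over. Only error in IL-6 is counted; error in walking-speed change would lower the correlation further but would not bias the slope. The point should be settled before analysis, since the strength of this relationship is a stated pilot goal and informs the main trial.

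**What to change.** In section 6.10.c:
- Define the predictor as change in log(IL-6), consistent with 6.10.b, and state the baseline and the follow-up time point. Reconcile this with the mixed-model wording in 6.10.d.
- Report the slope and correlation both as observed and corrected for reliability, using the within-person variance from the two screening draws (Aim a (iii)).
- State that -0.126 and -0.152 refer to measured change.
- Keep the mean of the 3-, 6-, 9- and 12-month draws as a sensitivity analysis only. It changes the estimand to average IL-6 over follow-up, and it can lose power if true change differs between visits, which is possible because the titration rules allow a dose change after month 6.

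In section 6.10.e, take the corrected estimate into the decision alongside the observed one.

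The cost is SAP wording, with no new data. The downside is that the corrected slope has a wider interval and depends on a within-person variance estimated in people selected by the IL-6 entry rule. That variance should be compared with the assumed 30% CV and the limitation stated.

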To address this gap in evidence, we will conduct the main randomized clinical trial (RCT) **ENRGISE (ENabling Reduction of low-Grade Inflammation in SENiors)** to test the ability of anti-inflammatory interventions for improving or preserving walking ability. We have maximized the public health impact of the interventions by selecting interventions that are safe, tolerable, acceptable, and affordable for vulnerable older persons. Based on an extensive literature review, we test the efficacy of the angiotensin receptor blocker (ARB) losartan (LO) and omega-3 polyunsaturated fatty acids (ω -3) as fish oil. To maximize the anti-inflammatory effect and potential benefit on mobility, we explore both individual and combination interventions that target different, but complementary and potentially synergistic anti-inflammatory mechanisms.¹²⁻¹⁵ We plan to recruit older persons at risk for, or with, mobility impairment, as measured by slow gait speed and self-reported mobility difficulty, and who have elevated blood levels of IL-6 (>2.5 pg/ml), the marker most consistently associated with mobility limitations.¹⁻⁷ Preliminary data on feasibility and information required for obtaining sample size estimates are needed to effectively design and implement the main trial. Thus, we implement the following **specific aims** for the ENRGISE Pilot Study:

- a. Conduct a pilot RCT in 300 older persons at risk of mobility decline to assess: (i) compared with placebo, the effects of LO, ω -3, and LO+ ω -3 on IL-6 and walking speed; (ii) the recruitment yields, the target population, adherence, retention, tolerability, sample-size, design, and cost for the main RCT; and (iii) the intra-subject variability of IL-6, and the dosage and safety of the interventions.
- b. Measure novel and established inflammatory markers to:
 - i. Characterize the effect of LO and ω -3 on these biomarkers and determine: (a) Are these cytokines/pathways impacted by the interventions? (b) Are the changes in these markers pre- vs. post-intervention less than, equivalent to, or greater than that of IL-6? and
 - ii. Assess if these biomarkers yield independent information from IL-6 with respect to change in walking speed and/or provide benefit for screening participants for the main trial.

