6.6. Recruitment – inclusion/ exclusion criteria - (details in Table 6.2.)

We identify men and women aged ≥ 70 years who are **able to complete the 400 m walk** at baseline, and are at **high risk of mobility disability** assessed by

- Self-reported difficulty walking ¼ mile or climbing a flight of stairs,
- Usual walking speed <1 m/sec and >0.44 m/sec on the 4 m walk (in the pilot phase we explore the feasibility of recruiting at least 50% of participants who have a baseline walking speed of <0.80 m/sec and >0.44 m/sec),^{22, 154, 155} and
- Chronic low-grade inflammation measured by IL-6 >2.5 pg/ml, the threshold we have found for increased risk of mobility limitation,^{1, 2} and <30 pg/ml to exclude high grade inflammation. To minimize within person variability,^{150, 156} IL-6 is the average of 2 measures taken at screening visits, with the first measure being >2.3 and <30 pg/ml, and the average of the two measures >2.5 and <30 pg/ml.

We exclude subjects with acute, autoimmune and HIV illnesses and causes of low walking speed that may be related to neurological conditions, severe arthritis, or low vitamin D. Other exclusion criteria reflect conditions that may interfere with the conduct of the study, interventions or assessments. Those taking ACEI or ARB are excluded from the LO randomization and those eating >2 servings/week of fish in the past year or taking fish oil are excluded from the ω -3 randomization. We recruit from the community. We use recruitment strategies successfully applied in LIFE,¹⁵⁷ LIFE-Pilot,¹⁵⁸ and TTrial,¹⁵⁹ which include primarily mass mailing, and newspaper, radio and TV ads and explore alternative recruitment strategies, such as electronic medical records to identify patients not taking study drugs and assess whether that strategy is effective in lieu of or in addition to mass mailing.

Table 6.2. Inclusion and exclusion criteria

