6.8. Screening, assessments and follow-up (Table 6.3.)

Potential participants are screened by telephone interviews to assess the main inclusion/exclusion criteria. Those who qualify are invited for the first screening visit during which a brief informed consent is obtained and the 4 m walk at usual pace is administered. Blood level of IL-6 is tested in those with a walking speed <1 m/sec and >0.44 m/sec. Participants with qualifying IL-6 levels are invited for the second screening visit to review medical history and current medications, complete blood testing (vitamin D, CBC, chemical panel, and second IL-6 measure), vital signs (blood pressure, pulse and temperature), 400 m walk, and the Mini Mental State Examination (MMSE).¹⁸⁵ The study medical safety officer will review the participant's health history, medication use, vital signs, and laboratory test results, and clear for randomization according to the study inclusion and exclusion criteria. If there are no safety concerns, participants attend the baseline visit during which the following is completed: full informed consent, questions to assess frailty,¹⁷¹ blood collection for labs, vital signs and anthropometric measurements, the SPPB, isokinetic dynamometry of the knee extensors and flexors, grip strength, and questionnaires. Validated Minnesota physical activity¹⁸⁶, depressive symptoms (CES-D)¹⁷⁵, patient reported outcomes (SF-36), and fatigability¹⁹⁸ questionnaires are completed at the baseline and 12 month visit. The physical activity results are used as potential modifiers in the data analyses. If there are no exclusion criteria identified, the participants are randomized, and the study drugs are dispensed. The baseline measures are repeated as outlined in Table 6.3. BP&P, blood tests and adverse events are measured about 1 week after randomization and after each visit when the LO dose is modified. Medication dose is adjusted as outlined in the above titration and safety algorithms.

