To assess intra-person variability in IL-6 (Aim a (iii)), we measure IL-6 at both screening visits. We use a Bland-Altman plot to assess agreement; this is summarized using a 95% CI of the difference at the two visits providing information on the expected differences over one week due to biological variability and measurement error. If agreement is high, one measure is likely sufficient for recruitment into the main study. If not, we may need to use two or more measures to determine eligibility and to assess participant-specific risk.

6.10.d. Additional inflammatory biomarkers:

In addition to IL-6 levels, we examine additional markers of inflammation (Aim b (i) and (ii)). As with IL-6, our primary focus is on the relationships between changes in cytokines with the change in walking speed using linear mixed models. We use stratified linear mixed models (as described above for IL-6) to examine the impact of interventions on these cytokines. These analyses assess whether changes in these cytokines are of similar magnitude to IL-6. As the absolute levels differ between cytokines, focus is on relative changes from baseline. We also examine these cytokines in models also including baseline and follow-up log(IL-6) to assess whether they provide additional predictive information. We also explore MMD event rates by baseline levels of IL-6 and additional cytokines to explore whether we can use an additional cytokine to select a population at greater risk to use for the main study, recognizing the potential tradeoff between ease of recruitment and selecting a population at higher risk.

6.10.e. Informing the main study

We assess compliance and retention rates (Aim a (ii)). Although we expect to be underpowered for incident mobility disability, we collect these data and compare estimates of event rates to those obtained in SA group LIFE participants that would have been eligible for ENRGISE (Aim a (ii)). While power is limited, we also examine whether there is sub-additivity and interaction of interventions in stratum 3, which supports the decision of whether to proceed with a factorial or parallel group design in Phase 3 (Aim a (ii)). .

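### The first of the two screening IL-6 draws used to measure one-week variability must pass an entry cut before the second is taken, which creates a false fall that the plan would read as biology and assay error

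*Combined protocol and SAP*

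**What the plan says.** Section 6.10.c sets the method: "To assess intra-person variability in IL-6 (Aim a (iii)), we measure IL-6 at both screening visits". Agreement is shown on a Bland-Altman plot, and "this is summarized using a 95% CI of the difference at the two visits". The result is taken to give the "expected differences over one week due to biological variability and measurement error", and it feeds a design choice: "If agreement is high, one measure is likely sufficient for recruitment into the main study". Otherwise the plan contemplates two or more measures.

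The same two draws decide entry. Section 6.6 defines the qualifying IL-6 as an average of two screening measures, "with the first measure being >2.3 and <30 pg/ml, and the average of the two measures >2.5 and <30 pg/ml". Section 6.8 puts the steps in order: "Participants with qualifying IL-6 levels are invited for the second screening visit". Nobody with a first value of 2.3 or below therefore contributes a pair.

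Section 6.10.c does not give the analysis set, the measurement scale or a threshold for high agreement. It does not say whether the 95% interval is for the mean difference or for individual differences. It does not mention the entry cut. Table 6.3 schedules IL-6 again at months 3, 6, 9 and 12, but the plan does not use those values for this aim.

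**The concern.** A lower cut on the first draw selects people whose first measurement error happened to be upward. The second draw carries a fresh error with no matching cut. The pair then differs on average although the person is stable. The requirement on the average treats the two draws symmetrically and would not by itself shift the mean difference, so the first-draw cut is the cause.

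Measuring intra-subject variability is part of Aim a (iii) and is goal 8 of the pilot (section 6.1). If the interval in section 6.10.c is for the mean difference, it largely measures the entry rule and says little about variability. If it means limits of agreement, those are shifted downward and slightly narrow. In either case, attributing the difference only to biology and assay error is wrong as written.

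**Working it through.** The plan gives no sample size, power or agreement figure for this analysis, so there is nothing of its own to reproduce.

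**Inputs from the documents**
- Within-person variability: section 6.2.a.1 says the SD of a person's "day to day variability is about 30% of the mean value". On the log scale, σw = √ln(1 + 0.30²) = 0.294.
- Entry rule: first draw 2.3–30 pg/ml, average 2.5–30 pg/ml (section 6.6).
- 300 enrolled pairs (section 4, Aim a).

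**Assumptions, not in the documents**
- Usual IL-6 is lognormal in the screened population, with median m of 2.0–3.0 pg/ml (4.2 as a sensitivity value) and between-person log SD σb of 0.4–0.6.
- Errors are independent, and there is no true change between visits.

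**Without selection.** The mean log difference is 0 and its SD is √2 × 0.294 = 0.415. The limits of agreement as a ratio are exp(±1.96 × 0.415) = 0.44 to 2.26. With 300 pairs the 95% CI of the mean is ±1.96 × 0.415/√300 = ±0.047.

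**Everyone with a second draw.** Let σ² = σb² + σw², ICC = σb²/σ², and α = (ln 2.3 − ln m)/σ. Ignoring the upper limit of 30, the expected second-minus-first log difference is

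−(1 − ICC) × σ × φ(α)/[1 − Φ(α)].

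| m, σb | 1 − ICC | σ | α | φ/(1 − Φ) | log difference | fall |
|---|---|---|---|---|---|---|
| 2.0, 0.4 | 0.350 | 0.496 | 0.282 | 0.985 | −0.171 | 15.7% |
| 2.5, 0.5 | 0.256 | 0.580 | −0.144 | 0.709 | −0.105 | 10.0% |
| 3.0, 0.6 | 0.193 | 0.668 | −0.398 | 0.563 | −0.073 | 7.0% |
| 4.2, 0.4 | 0.350 | 0.496 | −1.214 | 0.215 | −0.037 | 3.7% |

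The fall is 1 − exp(log difference). Simulation with the full rule gives the same range for medians of 2.0–3.0: a log fall of 0.07 to 0.17.

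**Enrolled people.** The added condition on the average has to be simulated (2 to 4 million people per setting).
- Mean log difference is −0.038 to −0.086, a fall of 3.7% to 8.2%. At a median of 4.2 the fall is 2.3% to 2.7%.
- SD of the log difference is 0.386 to 0.401 against 0.415: 1 − 0.386/0.415 = 7% and 1 − 0.401/0.415 = 3% too small.
- The ratio of fall to standard error with 300 pairs runs from 0.038/(0.401/√300) = 1.6 to 0.086/(0.386/√300) = 3.9. Nominal significance is likely over much of the range but not assured.

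**Check of the cause.** Selecting on the average alone gives a mean difference of 0.

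**Discordance between entry rules.** Take a one-draw rule of >2.5 (the plan states no cut for a single draw) against the protocol's sequential rule, with medians of 2.0–3.0. About 6–19% of one-draw passers have an average of 2.5 or below. About 4–8% of two-draw passers have a first draw between 2.3 and 2.5. No discordant case has a first draw of 2.3 or below.

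**The case against.** The strongest defence is that the artefact exists but does not touch the decision. A reader might infer that the pairs hide one of the two kinds of misclassification, because 8–17% of people with a true level above 2.5 fail the first draw and are never redrawn. The documents do not support that for the choice at issue. The protocol's two-draw rule is sequential, so a first value of 2.3 or below fails under it and fails equally under a one-draw >2.5 rule. Every case on which the two rules differ has a first value above 2.3 and is due a second draw. The hidden group matters only against the unobserved true level, or against a rule that always takes two draws. Against the latter, a one-draw rule's sensitivity would look like 92–98% in the selected pairs when it is 80–94% in everyone screened. Section 6.10.c proposes no such rule.

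A reader might also infer that selection biases the decision in a known direction. It does not. The false fall argues against agreement; the narrowed spread argues for it. With no threshold for high agreement, a changed decision cannot be shown. Under the 30% CV the limits are wide with or without selection: 0.44–2.26 unselected, against about 0.43–0.44 to 1.95–2.11 in enrolled people.

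The lower first cut of 2.3 softens the effect, the wording is hedged, and section 6.10.c does not restrict the analysis to randomised participants.

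Finally, replacing the screening pairs with placebo-arm follow-up draws could do more harm than good. The target is one-week variability and those draws are three months apart. Section 6.10.b gives a LIFE-P residual SD of 0.52 for log(IL-6), adjusted for baseline and treatment. Under a stable-level model that residual cannot exceed √2 × σw, so σw would be at least 0.52/√2 = 0.37, against 0.29 from the 30% CV. If drift explains that gap, the substitution adds more error than the 3–7% it removes.

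All of this stands. None of it makes the stated interpretation of the mean difference correct.

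**Conclusion.** The concern holds in a limited form. The first screening draw is truncated from below and the second is not, yet section 6.10.c attributes their difference wholly to biology and measurement error, and nothing elsewhere corrects this. The false fall is about 4–8% in enrolled people and 7–16% in everyone with a second draw, for medians of 2.0–3.0 pg/ml, between-person log SD of 0.4–0.6 and a 30% CV. It is about 2–4% at a median of 4.2. The spread in enrolled people is understated by only 3–7%.

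The size rests on an IL-6 distribution in the screened population that the documents do not give. Two stronger readings are not supported: that the one-draw-or-two decision is biased in a known direction, and that the pairs cannot show both kinds of disagreement between the candidate rules.

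**What to change.** Amend section 6.10.c as follows.

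1. Analyse log(IL-6) in everyone with a second draw, including those then found ineligible, not only the randomised.
2. State that the mean difference and limits of agreement are conditional on a first value above 2.3 pg/ml, and do not interpret the mean difference as a biological shift.
3. Estimate the within-person SD with a model that allows for the first-draw cut and uses all first draws, including those that failed. One route is maximum likelihood for a bivariate normal model of the log values, since whether a second draw is taken depends on the observed first value. As a simple check, regress the second log value on the first in everyone with a second draw. With equal variances, the slope estimates the ICC and the residual variance equals σw² × (1 + ICC). This check fails in the randomised subset, which is also selected on the average.
4. Report the within-person SD from placebo-arm draws at months 3, 6, 9 and 12, which played no part in entry, as a selection-free cross-check. Do not use it as a replacement, because three-month spacing adds drift. Table 6.1 plans about 90 placebo participants, so up to 90 × 3 = 270 degrees of freedom before missing data.
5. Base the one-draw-or-two choice on the within-person SD and on the observed discordance between a one-draw >2.5 rule and the sequential rule. Note that the exclusion of people whose true level exceeds 2.5 but whose first draw is 2.3 or below can only be estimated by model.

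No new samples are needed. The cost is a little more analysis, retention of screen-failure IL-6 values, and reliance on a distributional assumption for IL-6.
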